the subject is a minor the hardcopy will be provided to the parent. A study member is present during the consent process and he/she can pause, or make adjustments to volume and reading speed to subjects satisfaction. After the consent form has been read the subject will have the opportunity to ask questions.

- The waiting period will be as long as the prospective Subject requires.
- Patient will be asked at the start of every visit whether they wish to continue participating in LHON: Gene Therapy Clinical Trial.
- An investigator will also provide complete explanation of the study to potential participants and will ensure that all questions are answered prior to decisions about participation.
- Time that will be devoted to the consent discussion will as much time as potential participant requires.
- At the discretion of the potential participants, friends and/or family members will be included in these discussions. Subjects will be encouraged to ask questions prior to providing written informed consent. Participation in this clinical trial is completely voluntary and great care will be taken to ensure that individuals do not feel coerced to participate. Subjects will be able to terminate their participation at any time without prejudice.
- To ensure Subjects understand in participating in the clinical trial, subject will be asked questions regarding ICF.
- As the PI and co investigators speak only English no non-English speaking subjects will be enrolled to ensure communications between studies subjects and investigators.
- Patients who do not speak English will not be enrolled.
- Signatures will be obtained on an IRB approved assent form for all subjects ages 15-17 years old.

Waiver or Alteration of Consent Process (consent will not be obtained, required information will not be disclosed, or the research involves deception) – N/A

Subjects who are not 15 years old or older- Excluded

Cognitively Impaired Adults - Excluded

Adults Unable to Consent - Excluded

Adults Unable to Consent - Excluded

31) Process to Document Consent in Writing

After the patient is given verbal informed consent, he or she will be asked to sign the written informed consent form.

32) Drugs

Handling of Investigational Agent

The study agent will be stored according to regulatory guidelines (CFR 21, Part 312.69). The investigators will take adequate precautions, including storage of the investigational agent in a securely locked (**McKnight Building**) , substantially constructed cabinet or other securely locked (**Locked freezer**) to prevent theft or diversion of the substance into illegal channels of distribution. Only the PI has the key to this freezer.

Disposition of Study Agent

The investigators, in conjunction with the Research Pharmacy Services will maintain adequate records of the disposition of the drug, including dates, quantity, and use by subjects. If the trial is terminated, suspended, discontinued, or completed, the investigators will provide for disposition of the unused supplies, in accordance with regulatory guidelines (CFR 21, Part 312.62).

All requirements completed per FDA regulations

	Applicable to:
FDA Regulation	IND Studies
21 CFR 11	X
21 CFR 54	X
21 CFR 210	X
21 CFR 211	X
21 CFR 312	X
21 CFR 812	
21 CFR 820	

The FDA has given us approval for the low and medium dose injections. We will be supplying them pre-clinical data for the high dose injections before administering that dose to our patients with LHON. They have approved the injection procedure and our manual of procedures which we will follow according to all FDA regulations. In addition the Data Safety and Monitoring Committee constituted by the NIH will be reviewing our forms and data every 6 months.

33) Record Keeping

Accurate and complete study records will be maintained and kept in the
McKnight Bldg

34) Publication and Presentation Policy

A Study publication is one which contains details of the design, methods, or results of the Study, and is written by investigators. Any paper classified as a Study publication must be approved by the Data and Safety Monitoring Committee prior to submission for publication. Similarly, any presentation made on behalf of the Study must be approved by the Data Safety and Monitoring Committee.

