injected. If both eyes have the same acuity the eye with longest onset will be injected. If one eye has <12 months and >6month since onset and the difference in acuity between the eyes is ≤ 10 letters, the eye with ≥ 12 months will be injected. If eyes have an acuity difference >10 letters, the eye with worse acuity will be injected.

Aim 2. To Evaluate the Safety of AAV-ND4 in subjects with acute (<12 months) bilateral loss of visual acuity to ≤ 35 ETDRS letters (Snellen = 20/200) (Group 2). The eye with worse acuity will be injected.

Aim 3. To Evaluate the Safety of AAV-ND4 in subjects with unilateral loss of acuity to ≤ 35 ETDRS letters, but who have “good acuity” ≥ 70 letters (20/40 Snellen) in the contralateral eye (Group 3). The eye with better acuity will be selected for injection.

For each group, administration of study drug will follow an adaptive plan to identify the maximum tolerated dose. If none of the three subjects at a given dose level develops a major toxicity, the next cohort will receive the next higher dose. We will wait a minimum of 6 weeks between injections of the same dose in successive subjects, and will wait until 3 months after the last subject is injected with this dose before moving to the cohort receiving the next higher dose. We will test the lowest dose first in 3 subjects of Aim 1, before moving on to testing this low dose in Aim 2, then lastly in Aim 3. Safety will be monitored for loss of 15 letters in Aims 1 and 2, but a difference of 15 letters worse in the treated eyes relative to untreated eyes for Aim 3. If acuity, and visual field testing demonstrate no toxicity in Aims 1 and 2, we will proceed with Aim 3.

The **objective** of this proposed clinical trial is to evaluate the safety of mitochondrially targeted ND4 gene therapy with the adenoassociated viral vector in appropriate LHON patients in a Phase I clinical trial. If warranted by the results of the Phase I trial, another aim will be to obtain a preliminary estimate of the therapy’s efficacy. We provide a summary of the extensive preclinical testing in relevant rodent animal models to support the efficacy of the approach proposed in this clinical trial.

The **primary hypothesis** being tested is there will be no systemic toxicity or loss of vision to No Light Perception in the injected eye.

4) **Background***

Background and Significance

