9. History of neurodegenerative conditions (e.g. multiple sclerosis, neuromyelitis optica, Parkinson disease)
10. History of autoimmune conditions (e.g. systemic lupus erythematosus)
11. Systemic diseases having ocular manifestations likely to confound assessment of study resultsHistory of cancer within five years other than localized basal or squamous cell carcinoma not near the orbital area. Patients with a prior history of cancer will need documentation from their cancer specialist that the cancer was cured at least 5 years before study entry.
12. Allergy to pupil dilating drops or narrow angles precluding safe dilation.
13. No Light Perception (NLP) vision in either eye.

, “No special populations are to be included in this research, such as children 14 years old or younger, prisoners, or pregnant women.

- **Exclude:** All subjects who are unable to consent
- **Exclude:** Children 14 years old or younger
- **Exclude:** Pregnant women

- **Exclude:** Prisoners

6) **Number of Subjects***

Number of Study Centers: One (1), Bascom Palmer Eye Institute, University of Miami, Miami, FL.

For each group patient recruitment will consist of 3 cohorts, until the last cohort which will consist of both Group I and III individuals.

Table 1 Proposed Sample Size

	Low-dose (1.18×10^9 vg)*	Medium dose (5.81×10^9 vg)*	High dose (2.40×10^{10} vg)	Higher dose (1×10^{11} vg)
Group I	3	3	3	
Group II	3	3		3
Group III	3	3		
Group I And** Group III				3 3

*=based on CHOP titers as recommended by FDA

As summarized above, dose escalation will follow the adaptive Phase 1 plan of Rubinstein and Simon (<http://linus.nci.nih.gov/techreport/phaselctd.pdf>). At each dose, escalation will occur until 2 of 3 (or 6) injected eyes manifest the safety endpoint. (See reference for detailed description of dose escalation strategy) Table 2 of the reference contains operating characteristics of this approach. Following the algorithm of Rubinstein and Simon with three doses, the sample size could range between 3 and 18 for each group. As an example, if the true probabilities of noteworthy safety events in the proposed three doses were 0.05, 0.25, 0.5, respectively, the most likely sample sizes for each group would range between N=9 with probability 20%, N=12 with probability 54%, or N=15, with probability 22%. These sample sizes could potentially be sufficient to observe a treatment effect when compared in a matched fashion to the uninjected eyes in groups 1 and 3.

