**Escalation from high dose group I to higher dose group II was previously approved. Since chronic bilateral group I individuals are considered at lower risk than group II, there are no additional safety concerns to injecting group I intermixed with group III individuals, after the 3rd group II injection and 3 month safety period. In this combined cohort, each of the 6 injections will be spaced at least 6 weeks apart. Ordering of participants will be determined by their presentation to the study and PI discretion, with the aim of ensuring injection of the more difficult to recruit group III individuals.

7) **Study-Wide Recruitment Methods* N/A for Multi-center trial**

Number of Study Centers: One (1), Bascom Palmer Eye Institute, University of Miami, Miami, FL.

Phase I. A review of the LHON patients currently being seen by [REDACTED] and [REDACTED] with long-standing severe vision loss of 20/200 or worse, shows that we have 23 patients who would be eligible for the Phase 1 study in Groups 1 and 2. We expect that the availability of a potential treatment will draw more patients in groups 2 and 3. Thus, we should have a sizable pool of patients for the Phase 1 safety study of the AAV-ND4 vector.

Individuals who have been diagnosed with G11778A mutation associated Leber's hereditary Optic Neuropathy and who are eligible based on inclusion and exclusion criteria will be invited to participate in this clinical trial. A complete physical examination and clinical chemistries will be performed at a pre-treatment, screening evaluation to further determine eligibility. Subjects will be considered enrolled when they sign the Informed Consent.

Enrollment Procedures:

Eligibility will be assessed at a study team meeting prior to the baseline 2 exam. This meeting must include at least one MD coinvestigator in addition to the PI. Other participants may include clinical staff, biostatistics center staff, and the CRORS office. Minutes will be recorded during these meetings and a sign in sheet will be kept. If the injecting retina specialist is unable to attend the assessment meeting, they will be asked to review and sign off on the eligibility criteria checklist prior to the injection. If the patient meets all inclusion and exclusion criteria a request will be forwarded to the research pharmacist for Study Drug dilution.

8) **Study Timelines***

- The duration of an individual subject's participation in the study:10 years

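### The stagger between same-dose injections is time-only: no visible protocol text requires a single severe event to be reviewed before the next subject is injected

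*Combined protocol and SAP*

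**What the plan says.** Section 3 (Objectives, paragraph after Aim 3) sets the stagger within a dose: "We will wait a minimum of 6 weeks between injections of the same dose in successive subjects". The move to the next higher dose waits 3 months after the last subject at the current dose and requires that none of the three subjects has had a major toxicity. For the mixed Group I and Group III cohort at the Higher dose, the double-starred note to Table 1 in Section 6 repeats the time rule: "In this combined cohort, each of the 6 injections will be spaced at least 6 weeks apart". That cohort opens "after the 3rd group II injection and 3 month safety period". Its order is described as follows: "Ordering of participants will be determined by their presentation to the study and PI discretion".

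The numeric rule in Section 6 reads: "At each dose, escalation will occur until 2 of 3 (or 6) injected eyes manifest the safety endpoint". Section 3 also has a gate for Group III: "If acuity, and visual field testing demonstrate no toxicity in Aims 1 and 2, we will proceed with Aim 3". The primary hypothesis is that "there will be no systemic toxicity or loss of vision to No Light Perception in the injected eye".

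Review routes exist:
- Section 10: light perception is checked right after injection, with examinations on days 1 and 7.
- Section 12: safety events go to the FDA, the NEI and the DSMC. Ongoing monitoring of each patient feeds the decision on further recruitment. The DSMC reviews adverse events as it and the NEI see fit.
- Section 13: the DSMC meets at least twice a year, can confer by telephone and can terminate the study. Section 32 gives a 6-monthly review.
- Section 7: each new subject's eligibility is settled at a minuted meeting of the PI and at least one other physician.

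**The concern.** A stagger reliably protects the next subject only if the previous outcome must be looked at before that subject is dosed. Here the interval passes whether or not anything happened in it. One injected eye that loses light perception, or one severe systemic toxicity, would contradict the primary hypothesis, yet neither is stated to hold the next injection.

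This is a first-in-human, one-time gene transfer, so a subject injected too soon cannot be untreated. The stakes are highest in Group III, where "The eye with better acuity will be selected for injection" and that eye enters with at least 70 letters. In the combined cohort a Group III subject may be injected before Group I is complete at the highest dose.

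**Working it through.** **Step 1. What conditions the next same-dose injection?**
- Spacing (Sections 3 and 6): elapsed time only, at least 6 weeks.
- Major-toxicity rule (Section 3): governs the move to the next dose, not the next subject at the same dose.
- Numeric rule (Section 6): needs two events. It counts injected eyes, although the same section also speaks more generally of safety events and Section 12 lists systemic events among them. Whether systemic toxicity counts is therefore unclear.
- Aim 3 gate (Section 3): rests on acuity and field results in Aims 1 and 2. It can protect Group III from vision events seen in Groups I and II. As worded it does not cover systemic events, events arising in Group III, or successive subjects within Group I or II. It is not stated to be re-checked between injections in the combined cohort.
- Reporting, ongoing review and DSMC powers (Sections 12, 13 and 32): none carries a trigger or deadline tied to the next injection.
- Pre-injection meeting (Section 7): concerns the incoming subject's eligibility.

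**Step 2. Does a cohort end at three after one event?** Section 6 gives per-group sample sizes for event probabilities 0.05, 0.25 and 0.5: N=9 with 20%, N=12 with 54%, N=15 with 22%. These were enumerated exactly with binomial terms C(3,x)·p^x·(1−p)^(3−x) under this rule:
- 0 of 3 escalates; 1 of 3 adds three subjects; 1 of 6 escalates; 2 or more stops.
- After a stop, the next lower dose is filled to six if only three were treated there (one level down only). There is no confirmatory expansion at the top dose.

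Result: N=9 19.7%, N=12 53.7%, N=15 21.6% (remainder: N=3 0.7%, N=6 1.9%, N=18 2.4%). The stated figures reproduce. Variants with no step-down, two levels of step-down, or confirmation at the top dose each miss at least one of the three. The published figures therefore fit a rule in which one event in three brings three more subjects at the same dose, so a three-subject cohort can become six.

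**Step 3. How many injections fit before the guaranteed review?** Inputs: spacing 6 weeks (Section 3); guaranteed review twice a year, so T of about 26 weeks (Sections 13 and 32); up to six subjects (Section 6). Assumptions: minimum spacing, an event soon after injection, no ad hoc review and no second event. For an event in subject k:

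further injections = min(6 − k, floor(T/6))

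With T = 26, floor(26/6) = 4 (weeks 6, 12, 18, 24):
- Cohort expanded from three to six: k=1: min(5,4) = 4; k=2: min(4,4) = 4; k=3: min(3,4) = 3.
- Combined cohort of six as tabulated, Aim 3 gate not applying: 4, 4, 3, 2, 1 for k = 1 to 5.
- Combined cohort, gate applied after a Group I vision event: only the remaining Group I subjects count. With three tabulated, that is at most 2, 1 or 0 after the first, second or third.

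With T = 13, floor(13/6) = 2, so at most 2. With T under 6 weeks, none.

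**Step 4. Would the Group III acuity event work as a trigger?** The note to Table 6-6 sets it at 15 letters below the fellow eye's worst acuity to date. The fellow eye enters at 35 letters or fewer, so the threshold is at most 35 − 15 = 20 letters. From at least 70 letters, that is a loss of at least 70 − 20 = 50 letters. If the fellow eye has ever read 14 letters or fewer, the threshold is 14 − 15 = −1 or lower, which cannot be reached on the letter scale.

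**The case against.** The strongest reply is that the protocol puts clinical judgement above the numeric rule. Section 12 says that monitoring of each patient's course by the Biostatistics Center and the DSMC decides whether recruitment continues, with statistics only a guide. Loss of light perception is reported to the physician at once. The DSMC can confer by telephone at any time. The physicians who know of an earlier event sit in the meeting that clears the next subject. Continuing after one event is also a disclosed feature of the escalation plan.

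Much of this stands. A responsible team would probably pause, and the Section 12 monitoring is a real safeguard. What it lacks is a written trigger, a deadline and a link to the next injection. The disclosed escalation feature concerns whether dosing may go on after one event, not whether the event is reviewed first.

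A reader might infer more than the documents support:
- *That the trial has no hold.* Three sources cited in the protocol were not available: the Manual of Procedures, the escalation report, and the separate Biostatistics Center protocol from which Section 12 is abstracted. Any of them could contain one.
- *That severe events go unreviewed for six months.* Section 12 provides for reporting and ongoing review; only the guarantee is twice-yearly.
- *That systemic toxicity is excluded from the numeric stop.* That is one reading of an ambiguous text.
- *That at most two subjects are exposed in a three-subject cohort.* Possible expansion to six makes that too low as an upper bound.

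**Conclusion.** The point holds as a gap in the visible protocol text. Followed to the letter, the plan permits another irreversible injection, including into the better eye of a Group III subject at the Higher dose, before a single severe event has been reviewed.

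The size is illustrative: up to 4, 4 or 3 further same-dose injections after an event in subject 1, 2 or 3. This rests on the Step 3 assumptions, and earlier DSMC review or slower recruitment reduces it. It is a count of possible exposures, not a risk, because the documents give no expected event rate. The change should be made because it is cheap and the treatment cannot be reversed. Confidence is medium because of the unseen documents.

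**What to change.** State in Sections 3, 6 and 13 that the next injection in any group, including the combined cohort, is held until the DSMC has reviewed the event (by telephone conference if needed) after any of:

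1. loss of light perception in an injected eye;
2. a grade 3 or 4 ocular toxicity on Table 6-6 judged to threaten vision or the globe;
3. a grade 3 or 4 systemic toxicity on Table 6-7;
4. the protocol's own acuity safety event: a 15-letter loss in Groups I and II, or the vision-related SAE in Group III. Where the fellow eye has read 14 letters or fewer, trigger 1 or an earlier point set by the DSMC must cover the case.

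Require the Aim 3 gate to be re-checked before each Group III injection in the combined cohort, and say whether systemic toxicity counts toward the numeric stop. If a hold already exists in one of the documents not seen, carry it into this protocol.

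The cost is one or two sentences in each section, using the existing DSMC, reporting route, SAE definition and toxicity scales. The hold requires review, not stopping, so the escalation rule and its operating characteristics are unchanged. The downside is a short delay after a severe event.

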An Open-label Dose Escalation Study of an Adeno-associated Virus Vector (scAAV2-P1ND4v2) for Gene Therapy of Leber's Hereditary Optic Neuropathy (LHON) caused by the G11778 mutation in mitochondrial DNA.

NCT02161380

Date: February 9, 2019. IRB 20140248.

1) **Protocol Title**

An Open-label Dose Escalation Study of an Adeno-associated Virus Vector (scAAV2-P1ND4v2) for Gene Therapy of Leber's Hereditary Optic Neuropathy (LHON) caused by the G11778 mutation in mitochondrial DNA

SHORT TITLE: Leber's hereditary optic neuropathy (LHON): Gene Therapy Clinical Trial

IND NO.: 15941

IND SPONSOR: [REDACTED]

- LHON: Gene Therapy Clinical Trial is registered on the Clinical Trials.gov website (<http://clinicaltrials.gov>). Clinicaltrials.gov number: NCT02161380

2) **IRB Review History***

N/A

3) **Objectives***

Our goal is to test safety.

The **purpose** of this dose-escalation study is to assess the safety and tolerability of scAAV2-P1ND4v2 (abbreviated as AAV-ND4) gene replacement therapy in subjects confirmed with the G11778A mutation in mtDNA responsible for Leber's Hereditary Optic Neuropathy. Ocular and systemic toxicity will be assessed following vector administration to determine if there are adverse changes that may be associated with vector administration.

This first-in-man (FIM) clinical trial will assess safety, tolerability, and potentially efficacy of a single intravitreal injection in patient groups reflecting the acute, presymptomatic and chronic stages and manifestation of the LHON disease.

Aim 1. To Evaluate the Safety of AAV-ND4 in subjects with long-standing bilateral acuity loss (Group 1). Phase I will consist of an open-label, unilateral single-dose, intravitreal injection of AAV-ND4 per subject in a dose-escalation study investigating the safety of four vector doses (Low: 1.18×10^9 vg*, Medium: 5.81×10^9 vg*(*based on CHOP titers as recommended by FDA), High: 2.40×10^{10} vg and Higher: 1×10^{11} vg) in subjects with molecularly confirmed G11778A-mutated mitochondrial DNA. The bilateral chronic group will include patients with ≥ 12 months since onset in one eye and at least 6 months onset in the more recently affected eye. Both eyes must have acuity reduced to ≤ 35 letters. If both eyes have ≥ 12 months since onset, the eye with worse visual acuity will be

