- The duration anticipated to enroll all study subjects: 3 years
- The estimated date for the investigators to complete this study (complete primary analyses): 5 years after first patient has received administration of study agent.

9) **Study Endpoints***

Assessment of Primary Endpoint – Toxicity

The **primary safety endpoint** in this trial is the standard ocular examination. Toxicity will also be assessed by measurement of vision, hematology and serum chemistries, assays for vector genomes, reported subject history of any symptoms and adverse events.

Ocular. Routine eye examinations will be performed before and after vector administration, and surgeons administering the injections will be alert to injection administration related complications. The clinical ocular examinations for toxicity will include slit lamp examination, measurements of intraocular pressure (applanation tonometry or Tono-pen) and gonioscopy (as needed in cases of increased intraocular pressure to examine for anterior chamber abnormalities). Some potential ocular toxicities are included in Table 6-6 below. These are modifications of the Ocular/Visual Adverse Events tables of the Common Terminology Criteria for Adverse Events v3.0 (CTCAE), considering the LHON patient population and the circumstances of the intervention. Direct and indirect ophthalmoscopy and biomicroscopy will be the mainstay of the retinal examinations. Fundus photography (with infrared illumination) will also be taken to document fundus appearance.

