Systemic. Physical examination at regularly-scheduled time points will be performed by a medical practitioner to allow detection of and response to any acute symptoms. Complete blood count with differential, prothrombin time (with INR), partial thromboplastin time, serum chemistries, including measures of hepatocellular integrity and of renal function (including BUN and creatinine), and a urinalysis will be performed at baseline visit (serving also as a pre-injection evaluation) and on post-treatment evaluations. This testing will help detect toxicity in a number of organ systems. For research purposes measurements of neutralizing antibodies to human ND4 and AAV capsid components and cellular assays will be performed prior to and after vector administration as markers of the immune response. At each contact with the subject, information will be obtained on adverse events by specific questioning. Systemic toxicity will be graded based on the scale included in Table 6-6 and 6-7.

Table 6-6: Ocular toxicity scale

Toxicity	Grade 1	Grade 2	Grade 3	Grade 4
Keratitis (corneal inflammation / corneal ulceration)	Abnormal ophthalmologic changes only; intervention not indicated	Symptomatic ; medical intervention indicated	Symptomatic ; surgical intervention indicated	Perforation or blindness (worse than baseline visual function)*
Glaucoma	Elevated intraocular pressure (EIOP) warranting topical agent for intervention	EIOP requiring topical agents and oral agents for intervention	EIOP warranting operative intervention	EIOP uncontrolled, resulting in blindness (worse than baseline visual function)*
Cataract	Mild change from baseline, detected on ophthalmologic exam; not warranting intervention	Moderate change from baseline, detected on exam; not warranting intervention	Severe change from baseline, detected on exam; not warranting intervention	Severe change warranting operative intervention*
Uveitis	Mild anterior uveitis not warranting intervention	Moderate anterior uveitis warranting medical intervention	Severe posterior or pan-uveitis warranting medical intervention	Severe uveitis warranting operative intervention and threatening ocular integrity*
Vitreous hemorrhage	Mild hemorrhage detected on ophthalmologic exam; not warranting intervention	Moderate hemorrhage not warranting intervention	Severe hemorrhage warranting vitrectomy	Uncontrolled vitreous hemorrhage, threatening ocular integrity

Table 6-6: Ocular toxicity scale

Toxicity	Grade 1	Grade 2	Grade 3	Grade 4

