Retinal detachment	Localized and intervention not indicated	Not resolving but intervention not yet indicated	Operative intervention indicated	Operative failure threatening ocular integrity*

*

For group III, due to the natural history of LHON where visual loss is expected in the asymptomatic eye, a vision-related SAE will be considered a decrease in acuity in the injected eye to 0.3 logMAR units (15-letter equivalent) worse than the worst acuity measured in the uninjected fellow eye at the current or any prior study visit.

Table 6-7: Systemic toxicity scale

Grade	Definition
1	Mild toxicity, usually transient, requiring no special treatment and generally not interfering with usual daily activities.
2	Moderate toxicity which may be ameliorated by simple therapeutic maneuvers, and impairs usual activities.
3	Severe toxicity which requires therapeutic intervention and interrupts usual activities. Hospitalization may or may not be required.
4	Life-threatening toxicity which requires hospitalization.

Evaluation of Secondary Endpoint – Visual Function Changes

Visual function will be quantified prior to and after vector administration in order to determine whether vector administration affects visual

function. The main measure of visual function will include best corrected ETDRS visual acuity.

10) Procedures Involved*

Method of Assigning Subjects to Treatment Groups:

Subjects enrolled in the study will be assigned to disease groups based on disease manifestation and screening evaluation. All subjects in the study will receive active treatment (one injection of scAAV2-P1ND4v2) at the Low, Medium or High dose as explained in section 6, Number of Subjects.

Study Visits:

Table 6-4 outlines the schedule of planned study evaluations. Subjects will be enrolled and undergo baseline assessments prior to Day 0. Study agent administration which will occur on Day 0 and details of the procedure are included below.

Table 6-4 Study Visit Summary Procedures

Time point	Baseline		Day								Year				
	B1	B2	0	1	7	3	6	9	1	2	3	1.5	2	3	4-10
Informed consent/assent	■														
Blood test for G11778A mutation	■														
History and physical exam	■			■		■		■			■				
Electrocardiogram, chest X-ray		■													
Pregnancy test	■	■													
Vital signs monitoring	■	■	■	■											
Hematology, chemistry, urinalysis	■		■	■	■	■	■	■	■	■	■	■	■	■	■
Coagulation Panel		■													
AAV antibody and specific reactivity (ASR) measurement	■			■				■			■				

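### As written, the 15-letter loss rule cannot be triggered by Group 1 or 2 eyes that start below 15 letters (about 20/500) or off the chart

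*Combined protocol and SAP*

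**What the plan says.** Section 3 (Objectives) sets the acuity rule for Groups 1 and 2: "Safety will be monitored for loss of 15 letters in Aims 1 and 2". Section 12 (Data Analysis) takes acuity change from Baseline 2.

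For Group 1, "Both eyes must have acuity reduced to ≤ 35 letters"; Group 2 has the same ceiling. The only lower limit at entry is Section 5, exclusion 13: "No Light Perception (NLP) vision in either eye". Group 2 always has the worse eye injected. Group 1 usually does, except for tied acuity and for some patients with one eye between 6 and 12 months from onset.

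Under Section 10 (ETDRS Visual Acuity) the score is the number of letters read at 4 m plus 1 m, and a line with no letters read scores zero. Worse vision is recorded as count fingers (CF), hand motions (HM) or light perception (LP), with no letter or logMAR value.

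Section 6 gives the stopping rule: "escalation will occur until 2 of 3 (or 6) injected eyes manifest the safety endpoint". Section 3 lets Aim 3 go ahead if acuity and visual fields show no toxicity in Aims 1 and 2. At the top dose, Section 6 opens the mixed Group 1 and 3 cohort "after the 3rd group II injection and 3 month safety period".

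Acuity is not the only safeguard. The primary safety endpoint "in this trial is the standard ocular examination" (Section 9), and the primary hypothesis in Section 3 includes loss to NLP. For Group 3, the note under Table 6-6 defines a vision-related serious event as acuity "0.3 logMAR units (15-letter equivalent) worse than the worst acuity measured in the uninjected fellow eye at the current or any prior study visit".

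**The concern.** A loss rule works only if the eye has that much to lose. Section 4 describes LHON as settling at acuities below 20/200, and the injected eye is usually the worse one. Eyes near or under the bottom of the letter chart are therefore plausible, and the 15-letter rule cannot register decline in them.

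Two things are at stake. First, such eyes can look reassuring at the gate to Aim 3, where the better eye, at 70 letters or more, is injected. Second, Section 12 plans adverse event rates with 95% confidence intervals. Eyes that cannot score stay in the denominator and pull any acuity-event rate down, even after escalation is complete.

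The backstops are thinner in the same eyes. Table 6-6 as shown has no row for acuity loss itself. Vision worse than baseline appears only as a grade 4 outcome of keratitis ("Perforation or blindness (worse than baseline visual function") and of glaucoma. Section 10 calls for a visual field only where the eye can count fingers. It also says that the pattern electroretinogram (PERG) is lost once ganglion cells have degenerated, so PERG may have little room to fall in chronic eyes. Fields, PERG and OCT have no stated toxicity threshold.

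**Working it through.** **1. Scale.** Inputs: 35 letters = 20/200 and 70 letters = 20/40 (Section 3); 15 letters = 0.3 logMAR, or 0.02 per letter (note under Table 6-6). The line through these is logMAR = 1.7 − 0.02 × letters, with Snellen denominator 20 × 10^logMAR.

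- 35 letters: 1.7 − 0.70 = 1.00, or 20/200 (protocol's anchor reproduced)
- 70 letters: 1.7 − 1.40 = 0.30, or 20/40 (reproduced)
- 15 letters: 1.7 − 0.30 = 1.40, or 20/502
- 14 letters: 1.7 − 0.28 = 1.42, or 20/526

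**2. Largest possible loss** = Baseline 2 score − 0. From 15 letters it is 15, so the rule can just be met. From 14, 10 or 5 letters it is 14, 10 or 5. From 0 letters or an off-chart category it is 0. The rule is reachable only from 15 to 35 letters.

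**3. One eye followed through: 10 letters to LP.** The letter loss is at most 10, so the rule is not met. Vision is not NLP, so that criterion is not met. Table 6-6 as shown grades no acuity loss as such. At LP a field is no longer called for. No stated acuity criterion is met, although the fall is on record.

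**4. Group 3.** If the fellow eye's worst score is below 15, being 15 letters worse would need a negative score. The same floor applies.

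**5. Effect on stopping (illustration only).** I read the Section 6 rule as: stop at 2 or more of 3; if 1 of 3, treat 3 more and stop on any further event. Then P(stop) = P(2 or more of 3) + P(1 of 3) × P(at least 1 of the next 3). Let m eyes in each three be able to score, each with true risk p of a serious acuity loss. The other 3 − m register a loss with probability c × p, where c is the share caught by anything else, including NLP. All of p, c and m are assumptions.

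With p = 0.5 and c = 0.5:

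- m = 3: 0.500 + 0.375 × 0.875 = 0.828
- m = 2: 0.375 + 0.4375 × 0.8125 = 0.730
- m = 1: 0.250 + 0.46875 × 0.71875 = 0.587
- m = 0: 0.15625 + 0.421875 × 0.578125 = 0.400

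With p = 0.25 and c = 0.5, the same formula gives 0.400, 0.312, 0.222 and 0.138. With c = 1 there is no effect: 0.828 (or 0.400) throughout. With c below 0.5 the loss is larger.

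**6. Event rate.** If a share f of eyes cannot score, the highest 15-letter event rate that can be observed is 1 − f. For example, if 3 of 9 eyes could not score (an assumption), the ceiling is 6/9 = 67%.

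**7. Cost of counting category falls.** Suppose all three eyes in each set have a low baseline, and each has a chance q of a repeatable fall from noise or natural decline. Before any DSMC review, the stopping count is reached with probability:

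- q = 0.05: 0.00725 + 0.135375 × 0.142625 = 0.027
- q = 0.10: 0.028 + 0.243 × 0.271 = 0.094
- q = 0.20: 0.104 + 0.384 × 0.488 = 0.291

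**The case against.** The strongest reply is that the 15-letter rule is a monitoring rule and not the stopping definition. Escalation turns on major toxicity, the primary safety endpoint is the ocular examination, and every enrolled eye can still reach NLP. The gate to Aim 3 asks for clean visual fields as well as acuity. CF, HM and LP are recorded, adverse events are asked about at each contact, and Section 12 says that statistical considerations only guide the decision. A fall from 10 letters to LP would be in the record for the DSMC to see. This stands: monitoring is weakened, not absent.

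A rule for off-chart vision may also exist elsewhere. Section 21 refers to a Manual of Procedures. Section 12 is abstracted from a separate data protocol and mentions acuity-loss events described further on, with no clear definition following. Table 6-6 is broken in the available text, so an entry may have been lost. This also stands, and it limits the point to the protocol as supplied.

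Inclusion criterion 3 (able to perform visual and retinal function tests) may keep out some HM or LP eyes. It sets no letter limit, and an eye at 0 to 14 letters can be tested, so the gap remains.

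A reader might infer that a cohort made up entirely of such eyes could never stop a dose. The documents do not support that, because loss to NLP, examination findings and DSMC judgement can all still do so.

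**Conclusion.** The point holds for the protocol as supplied: the 15-letter rule cannot be triggered by a Group 1 or 2 injected eye that starts below 15 letters or off the chart. That part is arithmetic and needs no assumption beyond a score floor of 0 and no letter value for CF, HM or LP.

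The size of the consequence is not known. The documents give no baseline acuity distribution, no true risk, and no basis for how much the other signals would catch. The effect on stopping runs from none, if they catch every loss, to a large loss of sensitivity. The figures under the illustration show the shape only and are not estimates.

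A reader might also infer that dose escalation so far was unsafe or should be reopened. The documents do not support this. Section 6 records that the step to the higher dose in Group 2 was approved, no outcome data are given, and the text does not say whether the mixed cohort has opened. This is a cheap improvement worth making, held with medium confidence because the Manual of Procedures and the data protocol were not available.

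**What to change.** - For Group 1 and 2 eyes with Baseline 2 below 15 letters or off the chart, also count as an acuity safety event a fall to a lower recorded category (letters to CF, CF to HM, HM to LP, or any to NLP), confirmed on a repeat acuity test. Require DSMC review before it counts towards stopping.
- List the letter change from Baseline 2 for these eyes in the reports the DSMC already receives, so that a fall from 14 letters to 1 is seen although no category changes.
- Extend the Group 3 rule under Table 6-6 through the same categories when the fellow eye's worst score is below 15.
- Apply this to decisions still open and to final reporting only.
- If the Manual of Procedures or the data protocol already assigns off-chart values, cite that rule in the protocol and check that it covers eyes at 0 to 14 letters.

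Cost: protocol wording, a derived field from data already recorded, and one repeat test per suspected fall. The downside is noise. A drop from 1 letter to CF would count, and Group 2 eyes may decline naturally over several months. A few extra events will need DSMC review; without that review, false stopping could reach 2.7% to 29% under the assumed false-fall rates of 5% to 20%.
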